All adverse events (AEs) occurring from the start of treatment to the end of the observation period will be collected for patients whose observation period is 60 weeks or less. For patients whose observation period exceeds 60 weeks, all AEs will be collected until 60 weeks and thereafter only malignancies and AEs leading to discontinuation of treatment will be collected.

• Analysis for safety evaluation

In the safety analysis set, the onset of major adverse reactions (AEs considered by the physician to be related to this drug), incidence of adverse reactions (number/percentage of patients with adverse reactions), and incidence of adverse events per duration of exposure (100 × number of patients with adverse reactions / total duration of exposure / 100 person-years) will be set as primary analysis items. In addition, factors that may affect the onset of adverse reactions will also be examined by conducting subgroup analyses based on patient background and other factors.

• Analysis for effectiveness evaluation

In the effectiveness analysis set, the rate of remission based on partial Mayo score will be set as primary analysis items.

• Dosage and administration of this drug

For induction, the recommended dose of this drug is 10 mg administered twice daily (10 mg BID [bis in die]) for 8 weeks. If the response is inadequate after the 8 weeks course of treatment, another 8 weeks course may be administered.

For maintenance, the recommended dose is 5 mg twice daily (5 mg BID). If the response decreases during the maintenance, the dose level may be increased to 10 mg BID. Intractable patients for whom prior drug therapies (e.g., a TNF inhibitor) were ineffective may be treated with 10 mg BID.

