5.4. Subgroups

5.4.1. Subgroups by dose level

The following subgroups will be defined depending on the mean daily dose to evaluate the safety of this drug and the dose response of the safety in patients treated mainly at 10 mg BID:

• Subgroups by mean daily dose (patients treated mainly at 10 mg BID, patients treated at a higher dose level, patients treated at a lower dose level)

Among the patients in the SAS, those who were treated at a mean daily dose of 17 mg or higher will be defined as patients treated mainly at 10 mg BID.

Among the patients in the SAS, those who were treated at a mean daily dose of 15 mg or higher will be defined as patients treated at a higher dose level; similarly, those who were treated at a mean daily dose of <15 mg will be defined as patients treated at a lower dose level.

The mean daily dose should be calculated as:

Mean daily dose = (Total dose administered during the treatment period) / (Total number of days in the treatment period including non-dosing days)

• Patients treated for a long term

Among the patients in the SAS, those with a duration of treatment of >16 weeks are defined as patients treated for a long term.

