6.4. Covariates

Candidate covariates for the development of Serious infections (including Tuberculosis, Pneumonia, Pneumocystis pneumonia, Sepsis, and Opportunistic infection), Herpes zoster, and Malignancy considered in this study are shown below.

| Covariate | Serious infections | Herpes zoster | Malignancy |
|--------------------------------------|-----------------------|------------------|------------|
| Gender [reference: male] | 0 | 0 | 0 |
| Age [reference: <50 years] | 0 | 0 | 0 |
| Body weight [reference: <50 kg] | 0 | 0 | 0 |
| BMI [reference: <18.5 kg] | 0 | 0 | 0 |
| Duration of UC [reference: <2 years] | 0 | 0 | 0 |

NIS Protocol A3921248 Statistical Analysis Plan

Serious Herpes Covariate infections Malignancy zoster Severity of UC [reference: moderate] 0 Past history (Infections) [reference: absent] 0 0 Past history (Malignancy) [reference: absent] × X Past history (Lung disorder) [reference: absent] 0 × × Complications (Infections) [reference: absent] 0 0 X Complications (Malignancy) [reference: absent] 0 Complications (Hepatic function disorder) [reference: absent] 0 0 0 Complications (Hepatitis B) [reference: absent] X X 0 Complications (Hepatitis C) [reference: absent] X X 0 Complications (Renal impairment) [reference: absent] 0 \circ 0 Complications (Diabetes mellitus) [reference: absent] Ο 0 0 Smoking [reference: absent] 0 0 0 Family history of malignancy (including lymphoma) [reference: absent] Prior treatment with a 5-aminosalicylic acid preparation [reference: 0 0 0 absent] Prior treatment with steroid [reference: absent] 0 0 0 Prior treatment with an immunomodulator (azathioprine, 0 0 6-mercaptopurine) [reference: absent] Prior treatment with tacrolimus [reference: absent] Prior treatment with a biologic agent [reference: absent] 0 0 Baseline neutrophil count [reference: <2000/µL] 0 0 0 Baseline lymphocyte count [reference: <1000/μL] 0 0 \circ Prior vaccination with a herpes zoster vaccine [reference: absent] 0 0 × Prior vaccination with a pneumococcal vaccine [reference: absent] 0 Prior vaccination with a tuberculosis vaccine [reference: absent] 0 Prior vaccination with a pneumocystis jirovecii pneumonia vaccine [reference: absent] Prior vaccination with a hepatitis B vaccine [reference: absent]

o: Applied, ×: Not applied

Additional covariates may be included or some deleted after consideration based on an interim analysis of this study or emerging knowledge. If this will occur, this SAP will be revised.

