8.1.3. Binary variables

For binary variables, patients included in each binary category will be summarized in terms of n and proportion. The two-sided 95% confidence interval (CI) will be determined using an exact method if a CI should be determined for the proportion.

When comparisons of the proportion should be made between subgroups, their risk ratios (RRs) will be presented with corresponding 95% CIs. Each RR and its 95% CI will also be presented graphically (See Appendix 2).

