To evaluate the dose-response relationship concerning the safety of the treatment with this drug, the following analyses will be performed in the patients treated at a higher dose level defined in Section 5.4.1 and in the patients treated at a lower dose level. To eliminate the effect of including patients who discontinued treatment during the induction phase, similar analyses will also be performed in patients treated at a higher dose level for a long term and in patients treated at a lower dose level for a long term:

• Adverse reactions of each element in the safety specification will be summarized in terms of number and proportion of patients as well as incidence and its 95% CI. In addition, the risk ratio and risk difference with their 95% CI will be presented for the patients treated at a higher dose level compared with those at a lower dose level.

• Adverse reactions will be summarized by SOC and PT in terms of number and proportion of patients.

In addition, to investigate the temporal change in the risk of the occurrence of each event, the following analyses will be performed in the patients treated at a higher dose level and patients treated at a lower dose level:

[figure not shown]
- Patients who experienced adverse reactions of each element in the safety specification will be summarized by timing of first onset, in terms of n and proportion as well as incidence and its 95% CI. As for the denominator to calculate the proportion, the denominator to calculate the incidence, and the categories used for onset timing, the corresponding descriptions in (1) should be followed.
- A Kaplan-Meier plot will be presented for the time to first onset of any adverse reaction included in each element in the safety specification.

• Subgroup analyses regarding patient characteristics

According to Section 8.1.3, the risk ratio based on the proportion of patients who experienced adverse reactions of each element in the safety specification will be determined and graphically presented for different subgroups regarding each of the patient factors defined in Section 8.2.2 in which events developed in ≥ 10 patients. Risk ratios will not be calculated for subgroups in which events developed in < 10 patients.

For each relevant subgroup defined in Section 5.4.2, patients who experienced adverse reactions will be summarized by SOC and PT in terms of n and proportion.

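### The safety dose-response contrast is unadjusted, although the SAP links 10 mg BID in maintenance to failed prior therapy or decreasing response

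*SAP*

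**What the plan says.** SAP 5.4.1 divides the safety analysis set by dose averaged over the whole treatment period. Those with "a mean daily dose of 15 mg or higher will be defined as patients treated at a higher dose level"; those below 15 mg form the lower-dose group.

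SAP 8.2.3.3(2) uses this split to evaluate dose response. For adverse reactions in each element of the safety specification it gives counts, proportions and incidence, and then "the risk ratio and risk difference with their 95% CI will be presented for the patients treated at a higher dose level", against the lower-dose group. The general method in SAP 8.1.3 says of subgroup comparisons only that "their risk ratios (RRs) will be presented with corresponding 95% CIs". Neither section names a stratum, covariate, weight or model.

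The one safeguard stated for the dose comparison is a repeat in patients treated for more than 16 weeks. Its purpose is given as "To eliminate the effect of including patients who discontinued treatment during the induction phase".

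On how dose is chosen, SAP 2.1 gives 5 mg BID as the recommended maintenance dose and adds two routes to the higher one: "If the response decreases during the maintenance, the dose level may be increased to 10 mg BID", and "Intractable patients for whom prior drug therapies (e.g., a TNF inhibitor) were ineffective may be treated with 10 mg BID". It also gives 10 mg BID as the recommended induction dose for every patient and allows a second 8-week course after inadequate response.

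SAP 6.4 opens with "Candidate covariates for the development of Serious infections" and goes on to herpes zoster and malignancy. Prior biologic treatment and age are both in its list.

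**The concern.** The SAP ties the higher maintenance dose to harder-to-treat disease and separately treats prior biologic use as a possible risk factor for safety events. A factor that may influence both dose and risk confounds a crude comparison of dose groups. A ratio above 1 could then come partly or wholly from treatment history, and a ratio near 1 could hide a dose effect if some other imbalance ran the other way. Since the section is presented as an evaluation of dose response, either result could be read as evidence about dose in a report that supports re-examination. Better classification of dose would not remove this problem.

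**Working it through.** **1. The plan's own figure.** There is none for this contrast. The planned 470 patients were set for a single-cohort herpes zoster rate (Protocol 7.5.2). The documents state no expected risk ratio, power or covariate distribution by dose group, so the size of any bias can only be illustrated.

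**2. Size of confounding when dose has no effect.** Let pH and pL be the shares of higher- and lower-dose patients with prior treatment failure, and r the factor by which prior failure multiplies risk. The crude ratio is then

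(pH·r + 1 − pH) / (pL·r + 1 − pL).

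All inputs are assumed.

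| pH vs pL | r = 1.5 | r = 2 | r = 3 |
|---|---|---|---|
| 0.6 vs 0.4 | 1.3/1.2 = 1.08 | 1.6/1.4 = 1.14 | 2.2/1.8 = 1.22 |
| 0.7 vs 0.3 | 1.35/1.15 = 1.17 | 1.7/1.3 = 1.31 | 2.4/1.6 = 1.50 |

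A more extreme split of 0.8 vs 0.2 with r = 3 would give 2.6/1.4 = 1.86.

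**3. Who enters the higher-dose group.** Take the SAP 2.1 schedule without interruptions: D weeks of induction at 20 mg/day, then 10 mg/day. After T weeks the mean daily dose is 10 + 10·D/T.

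- D = 8: the mean is at least 15 mg when 80/T ≥ 5, so T ≤ 16 weeks.
- D = 16: the mean is at least 15 mg when 160/T ≥ 5, so T ≤ 32 weeks.
- At T = 60 the means are 10 + 80/60 = 11.3 mg and 10 + 160/60 = 12.7 mg.

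In the full safety analysis set, anyone who stops by week 16 on the standard schedule therefore counts as higher dose, whatever their history. The restriction to more than 16 weeks removes those patients. It keeps as higher dose the patients who had a second induction course after inadequate response and stopped in weeks 17 to 32, and those who spent long enough in maintenance on 10 mg BID. These are the groups for which SAP 2.1 links dose to response or prior failure.

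**4. Precision available.** At the plan's assumed zoster rate of 8/100 person-years, and an assumed mean exposure of 0.35 to 1.0 years per patient, expected events are 470 × 0.08 × 0.35 = 13.2 up to 470 × 0.08 × 1.0 = 37.6. With an even split of 235 per group and equal risk p, the standard error of the log ratio is √[2(1 − p)/(235p)].

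- p = 13.16/470 = 0.028: SE 0.54, 95% CI around 1 of 0.34 to 2.90.
- p = 0.08: SE 0.31, 95% CI 0.54 to 1.85.
- 10 events in all (p = 10/470 = 0.0213): SE √(2 × 0.979/5) = 0.63, 95% CI about 0.29 to 3.41.

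Stratifying on two binary factors is feasible for the commoner elements. A model with many covariates is not.

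**The case against.** The strongest case against is that this is a secondary summary in a single-cohort surveillance study with no decision rules (SAP 4.2), and that readers will be able to see imbalance. SAP 8.2.2 already tabulates patient characteristics by mean-dose subgroup, both overall and in long-term patients. SAP 8.2.3.3 also gives single-factor risk ratios for the characteristics where events occurred in at least 10 patients. A bias of 1.08 to 1.50 is small beside the intervals in step 4. All of this is correct and limits the weight of the point. But the table and the single-factor ratios only show imbalance or risk by factor; they do not adjust the dose ratio.

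Two more objections stand. Two of the SAP 2.1 links to 10 mg BID, inadequate response after induction and decreasing response in maintenance, arise after baseline, and stratifying on baseline factors does not remove them. The documents also do not link age to dose. Age is proposed because SAP 6.4 marks it as a candidate covariate for all three listed outcomes.

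A reader might go further than the documents allow in three ways:

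- That the SAP directs 10 mg BID to patients who failed earlier therapy. Its wording is permissive, and 10 mg BID is also the induction dose for everyone, so dose group is not simply assigned by refractoriness.
- That dose effect and patient risk cannot be separated. This is true of the planned ratio only. Prior biologic use and age are collected, so a partly adjusted estimate is possible.
- That the SAP makes no use of its covariates. The single-factor ratios use several of the same characteristics, and SAP 7 mentions multivariate analyses, although no model appears in the visible text of Section 8. The narrower statement is that none of them adjusts the dose contrast.

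The blacked-out hypotheses text in SAP 4.1 and the figure not shown in 8.2.3.3 are not counted as gaps. The table in 6.4 is broken, so the outcomes for which prior biologic is marked cannot be read.

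**Conclusion.** The planned dose-response risk ratio and risk difference are crude and open to confounding by the reason for dose choice, on the SAP's own description of dosing. The repeat beyond 16 weeks does not address this. The illustrated range of about 1.08 to 1.50 with no dose effect rests wholly on assumed prevalences and risk multipliers; neither the size nor the direction of the actual bias can be derived from the documents. The analysis is worth improving because the data are already collected and the section is labelled as dose response. It is not the study's primary safety analysis, and stratification would reduce the problem without removing it.

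**What to change.** In SAP 8.2.3.3(2), for both the full safety analysis set and the set treated for more than 16 weeks:

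- Keep the crude risk ratio and risk difference.
- Add Mantel-Haenszel versions with 95% CIs, stratified by prior biologic (absent/present) and age (<65/≥65 years), both already defined in SAP 5.4.2. In stratum i let a and b be the patients with events in the higher- and lower-dose groups, n1 and n0 the group sizes, and N = n1 + n0. The ratio is Σ(a·n0/N) / Σ(b·n1/N), and the difference is Σ[(a·n0 − b·n1)/N] / Σ(n1·n0/N). State how patients with unknown prior biologic use, a category in SAP 8.2.2, are handled.
- Do this for elements with events in enough patients, for example at least 10, the threshold SAP 8.2.3.3 uses for its single-factor ratios. At that number the estimate can be computed but is imprecise. Below it, give the crude figure alone and label it unadjusted.
- Cross-refer to the SAP 8.2.2 table by mean-dose subgroup; no new table is needed.
- State that the crude and the stratified contrasts are both descriptive, and that neither removes confounding from inadequate or lost response during treatment.

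The cost is SAP wording and a few estimates from data already collected. Intervals become slightly wider, precision stays limited, and rare elements remain unadjusted.

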7.2.5. Observation period

The duration of observation will be 60 weeks (14 months) from the date of treatment commencement (Day 1). However, patients who are treated with XELJANZ for more than 60 weeks after the date of treatment commencement will be continuously followed up until the end of the investigation period * (June 2021). For patients who discontinue XELJANZ, information until the discontinuation will be collected.

*: Date of the last observation before June 2021

This study will be conducted using booklet type CRF. Investigator will complete each booklet of CRFs for each observation period in Table 1. However, for patients who discontinue XELJANZ, information until the discontinuation will be collected.

Name of CRF	Observation period
Booklet 1	Treatment commencement to Week 26 (Month 6) of treatment
Booklet 2	Week 27 (Month 7) to Week 60 (Month 14) of treatment
Booklet 3	Week 61 (Month 15) to end of the investigation period (June 2021)

Table 1. Name of CRF and observation period

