2.1. Study Design

This is a multicenter cohort investigation to be conducted in patients with ulcerative colitis treated with XELJANZ in clinical settings.

• Registration criteria

Patients must meet all of the following inclusion criteria to be eligible for inclusion in the study:

- •Patients with ulcerative colitis treated with XELJANZ
- •Patients naive to XELJANZ in the treatment of ulcerative colitis
- Sample size

470 to be collected in the safety analysis set (495 to be registered*)

• Rationale

Based on the results of clinical studies conducted up to approval, the incidence of herpes zoster in Japanese patients with ulcerative colitis chronically treated with XELJANZ was higher than that in the overall population of the studies. Therefore, on the assumption that the true incidence of herpes zoster in Japanese patients with ulcerative colitis is 8/100 person-years, the sample size will be 470 when the probability of the lower limit of 95% confidence interval for the incidence of herpes zoster not falling below 4/100 person-years (results for the overall population of the studies) is 80%.

- *: If it is assumed that 5% of the registered patients are unevaluable for the safety due to failure to show up or other reasons, 495 patients need to be registered to ensure that 470 patients are included in the safety analysis set.
- Safety specification

Important Identified Risks

- Serious infections (including tuberculosis, pneumonia, pneumocystis pneumonia, sepsis, opportunistic infection)
 - Herpes zoster
 - Neutropenia, lymphopenia, oligochromemia
 - Hepatic impairment
 - Reactivation of hepatitis B virus
 - Gastrointestinal perforation
 - Interstitial lung disease
 - Venous thrombosis
 - Malignant tumor
 - Cardiovascular event

Important Potential Risks

• Rhabdomyolysis, myopathy

Important Missing Information

Not applicable.

• Observation period

Each patient will be observed for 60 weeks from the start day of the treatment with this drug. Patients treated with this drug for more than 60 weeks will, however, be observed to the end of this study (June 2021). For patients who discontinued the treatment with this drug, data will be collected until the discontinuation.

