8.1.5. Analyses of time-to-event data

Kaplan-Meier plots will be presented for time-to-event data. Event-free patients will be censored at the end of their observation period or 60 weeks after the start of treatment, whichever came first. If the time to event exceeds 60 weeks, the patient will be treated as event-free and censored at 60 weeks. For malignancy, however, no such upper limit will be set for the time to onset, and malignancy-free patients will be censored at the end of their observation period.

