8.2.3. Safety analyses

Adverse reactions or AEs included in a summarization will be those that developed from the start of treatment to the end of the observation period or 60 weeks after the start of treatment, whichever came first, except for malignancy, for which all events occurring by the end of observation period will be included in a summarization. All adverse reactions and AEs reported in this study will be included in a listing.

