10. APPENDICES

10.1. Appendix 1: Details of Data Handling

A1.1 Definition of Study Visits 1

For the endpoints the partial Mayo score, stool frequency subscore, rectal bleeding subscore, and physician's global assessment subscore, the study visits are defined as follows:

| Visit | Definition [time window] |
|------------------|---|
| Baseline | From 6 months before Day 1 (= the day of first dose of Xeljanz in |
| | this study = the day of the start of treatment) to Day 1 (pretreatment) |
| Week 2 | Day 2 to Day 22 |
| Week 4 | Day 23 to Day 43 |
| Week 8 | Day 44 to Day 71 |
| Week 12 | Day 72 to Day 99 |
| Week 16 | Day 100 to Day 141 |
| Week 24 | Day 142 to Day 197 |
| Week 32 | Day 198 to Day 253 |
| Week 40 | Day 254 to Day 309 |
| Week 48 | Day 310 to Day 379 |
| Week 60 | Day 380 to Day 463 |
| End of treatment | From 2 weeks before to 2 weeks after the day of last dose |
| | If the day two weeks before the last dose is Day 1 or earlier, the time |
| | window is from Day 2 to 2 weeks after the day of last dose. |

A1.2 Definition of Study Visits 2

For the endpoints the Mayo score, findings of flexible sigmoidoscopy subscore, and faecal calprotectin, the study visits are defined as follows:

[figure not shown]
| Visit | Definition [time window] |
|----------|--|
| Baseline | From 6 months (or 3 months for faecal calprotectin) before Day 1 (= |
| | the day of first dose of Xeljanz in this study = the day of the start of |
| | treatment) to Day 1 (pretreatment) |
| Week 8 | Day 2 to Day 85 |
| Week 16 | Day 86 to Day 141 |
| Week 24 | Day 142 to Day 197 |

| Visit | Definition [time window] | | |
|------------------|---|--|--|
| Week 32 | Day 198 to Day 253 | | |
| Week 40 | Day 254 to Day 309 | | |
| Week 48 | Day 310 to Day 379 | | |
| Week 60 | Day 380 to Day 463 | | |
| End of treatment | From 2 weeks before to 2 weeks after the day of last dosing | | |
| | If the day two weeks before the last dose is Day 1 or earlier, the time | | |
| | window is from Day 2 to 2 weeks after the day of last dose. | | |

10.2. Appendix 2: Example of Tabulated and Graphical Presentations of Risk Ratios Regarding the Proportion of Patients with an Adverse Reaction in Different Subgroups

| 事象名: XXXの上昇 | 区分1 | | 区分2 | | リスク | リスク比 (RR) | |
|---------------------|----------|---------|----------|-------|------|---------------|--|
| | 例数/N | (%) | 例数/N | (%) | RR | 95 %CI | |
| 性別(男性 vs. 女性) | 18/2220 | (8.0) | 3/1099 | (0.3) | 2.97 | (0.88-10.06) | |

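### Patient-factor risk ratios use crude proportions although follow-up ends at discontinuation, so unequal time on treatment can distort them or mask a real effect

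*SAP*

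**What the plan says.** For the patient factors listed in SAP 8.2.2, section 8.2.3.3 says "the risk ratio based on the proportion of patients who experienced adverse reactions of each element in the safety specification will be determined", provided that events developed in at least 10 patients. It points to 8.1.3: "When comparisons of the proportion should be made between subgroups, their risk ratios (RRs) will be presented with corresponding 95% CIs". That section contains no person-time term, and the Appendix 2 template shows event patients over all patients for each category.

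Follow-up is tied to treatment. Protocol 7.2.5 states: "For patients who discontinue XELJANZ, information until the discontinuation will be collected". SAP 2.1 repeats it: "For patients who discontinued the treatment with this drug, data will be collected until the discontinuation". Under SAP 8.2.3, events are counted "from the start of treatment to the end of the observation period or 60 weeks after the start of treatment, whichever came first". Malignancy is the exception, "for which all events occurring by the end of observation period will be included in a summarization", and in 8.1.5 "malignancy-free patients will be censored at the end of their observation period". The investigation period ends in June 2021.

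The SAP has exposure-based tools. Section 8.1.4 defines person-year incidence with an exact interval, and 8.1.5 defines Kaplan-Meier plots with censoring. Incidence is applied to the whole safety set (8.2.3.1, 8.2.3.2). The dose subgroups in 8.2.3.3 get incidence, 15-week onset bands, Kaplan-Meier plots and a repeat analysis in patients treated for more than 16 weeks. The patient factors get none of these. Section 6.4 lists candidate covariates for three outcomes and section 7 mentions univariate and multivariate analyses, but the visible text of section 8 specifies no model.

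**The concern.** Protocol 7.7.2.1 relies on subgroup analyses to find factors that may affect the onset of adverse reactions. In the visible text, the crude risk ratio is the only comparative measure specified for patient factors. A patient who stops after three weeks and one who is treated for 60 weeks count equally in its denominator, although the first had far less time in which an event could be recorded.

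The factors in 8.2.2 include severity, refractory disease and prior biologic use. The stopping reasons in Protocol 7.3.10 include inadequate effect, remission and non-attendance. A link between such a factor and time on treatment is plausible in either direction. If there is one, a factor with no effect on risk can appear to have one, and a real risk factor can be missed. The results feed the re-examination application and proper-use material (SAP 3, Protocol 5).

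**Working it through.** **1. Is the planned statistic really crude?** Appendix 2, gender row: 18/2220 vs 3/1099.
- RR = (18/2220)/(3/1099) = 2.97.
- SE of ln RR = √(1/18 − 1/2220 + 1/3 − 1/1099) = 0.6225.
- 95% CI = 2.97 × exp(±1.96 × 0.6225) = 0.88 to 10.06, as printed.

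All nine readable rows with a ratio reproduce to two decimals in this way. Exposure does not enter.

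**2. Inputs for size.**
- From the documents: event rate h = 0.08 per year (herpes zoster, SAP 2.1) and cap T = 60/52.18 = 1.150 years.
- Assumed, because the documents give no figures by factor: stopping rate m per year, exponential and independent of the event, with the same h in both groups.
- Proportion with an event: p = h/(h+m) × (1 − exp(−(h+m)T)).
- Mean exposure: (1 − exp(−(h+m)T))/(h+m).

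**3. Constant hazard, no true effect.**

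| Stopping rate/year, factor vs reference | Not stopped by week 60 | Mean exposure, weeks | p | Crude RR | Rate ratio |
|---|---|---|---|---|---|
| 0.6 vs 0.3 | 50% vs 71% | 42 vs 49 | 0.0638 vs 0.0745 | 0.86 | 1.00 |
| 1.2 vs 0.3 | 25% vs 71% | 31 vs 49 | 0.0482 vs 0.0745 | 0.65 | 1.00 |
| 2.0 vs 0.5 | 10% vs 56% | 23 vs 44 | 0.0349 vs 0.0671 | 0.52 | 1.00 |

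**4. Front-loaded hazard, no true effect.** Assume three times the 60-week average in weeks 0-16, i.e. 0.24 per year. To keep the same total, the rate afterwards is (0.08×60 − 0.24×16)/44 = 0.0218 per year.

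| Stopping rate/year | Crude RR | Single unstratified rate ratio |
|---|---|---|
| 0.6 vs 0.3 | 0.93 | 1.09 |
| 1.2 vs 0.3 | 0.82 | 1.27 |
| 2.0 vs 0.5 | 0.74 | 1.43 |

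At twice the average in weeks 0-16, the crude ratios are 0.90, 0.74 and 0.64 and the rate ratios 1.05, 1.14 and 1.23.

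**5. Dilution and masking (constant hazard, assumed 60-week retention, reference vs factor).**
- True hazard ratio 1.25, 80% vs 50%: 0.0789/0.0789 = 1.00.
- True hazard ratio 1.5, 80% vs 30%: 0.0760/0.0789 = 0.96.
- True hazard ratio 2.0, 80% vs 50%: 0.1225/0.0789 = 1.55.

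**6. Stopping caused by the event itself.** The event is still counted. With hazard ratio 2 and no other stopping, RR = (1 − exp(−0.16T))/(1 − exp(−0.08T)) = 0.168/0.0879 = 1.91, so little is lost.

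**7. Chance of a misleading interval.** With an assumed 235 vs 235 split of the 470 patients and equal constant hazards, simulation puts the crude 95% CI wholly below 1 in 2.3% of studies at equal 80% retention, 8% at 80% vs 50%, and 20% at 80% vs 30%. Expected events in the last case are about 19 and 12, so the 10-event rule does not prevent it.

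**The case against.** The crude percentage of patients with adverse reactions is itself a primary item of the protocol, and SAP 4.2 sets no decision rules. An on-treatment risk ratio is a legitimate description, and the difficulty arises only when it is read as the effect of a factor. That stands, and it is why the crude ratio should be kept. But Protocol 7.7.2.1 gives the subgroup analyses exactly that second purpose.

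The sizes rest on assumed stopping rates, two of the three scenarios have a fourfold difference, and the mildest gives only 0.86. With 235 patients per group that is about 15 vs 18 events, with an approximate CI of 0.44 to 1.67, so the shift is small beside sampling error. This stands for that scenario. In the most extreme one the factor group expects only about 8 events (235 × 0.0349), so the 10-event rule, if applied to each subgroup, might suppress the ratio.

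A reader might infer that factors linked to early stopping will look protective. The documents do not support that. No section says which factors shorten treatment, patients with few alternatives might stay on longer, stopping caused by the reaction costs little, and a harmful factor may only be diluted. A reader might also quote a large malignancy bias: 3.1 years vs 60 weeks of observation at equal low hazard gives about 0.37. That ratio may never be produced. Ten malignancy reactions in 470 patients need about 1.4 per 100 person-years (10/(470 × 1.5)) if mean follow-up is 1.5 years, which is an assumption.

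**Conclusion.** The point holds as a conditional one. The patient-factor comparison ignores exposure, follow-up ends with treatment, and methods that the SAP applies to the dose subgroups are not carried over. The covariate list in 6.4 shows that factor modelling was contemplated, but does not fill the gap.

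The existence of the mechanism is certain. Its direction and size for any given factor are not. Under the assumed stopping rates and no true effect, the crude ratio ranges from 0.52 to 0.86 with a constant hazard and from 0.74 to 0.93 with the threefold early hazard. The sign reverses if the factor lengthens observation.

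A reader might conclude that the risk ratio should simply be replaced by one person-year rate ratio. The calculations do not support that. It is unbiased under a constant hazard, but with the threefold early hazard it lies further from 1 on the log scale than the crude ratio in all three scenarios. The SAP itself allows for risk that changes over time, since it plans onset bands and Kaplan-Meier plots for that purpose. The whole-cohort incidence estimates are unaffected by this point. What is at risk is the reading of individual factors.

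**What to change.** In SAP 8.2.3.3 and Appendix 2:
- Keep the crude risk ratio and label it as descriptive.
- For each patient factor, under the same 10-event rule, add the 8.1.4 incidence with its 95% CI by subgroup.
- Add a time-to-event comparison with the 8.1.5 censoring rules: either a Cox hazard ratio with a Kaplan-Meier plot, or a rate ratio stratified by the existing 15-week onset bands (extended beyond 60 weeks for malignancy, as already defined).
- State that conclusions about risk factors rest on that comparison, and do not substitute a single unstratified rate ratio.

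Onset dates and treatment dates are already collected and person-years are already derived, so no new data are needed. The cost is SAP wording, modest extra programming and a wider table.
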